3.13 Gantt Chart: (Timetable for research activity)	25
● References	26

List of Abbreviations

CP	Cerebral Palsy
GMFM-66	Gross Motor Function Measure-66
ROM	Range of Motion
RCT	Randomized Controlled Trial
PT	Physical Therapy
QoL	Quality of Life
SPSS	Statistical Package for Social Science
WHO	World Health Organization
MFR	Myofascial Release
MoH	Ministry of Health
UNRWA	United Nations Relief and Works Agency

Chapter One: Introduction

1.1 Introduction

Cerebral palsy (CP) is a group of permanent movement and posture disorders caused by non-progressive disturbances in the developing fetal or infant brain (Odding et al., 2006). It is the most common motor disability in childhood, often associated with spasticity, muscle weakness, and impaired coordination. These neuromotor deficits contribute to a spectrum of functional limitations, varying in severity and presentation across individuals. Children with CP often experience abnormal muscle tone, joint contractures, and impaired motor control, making functional mobility a significant challenge (Odding et al., 2006).

Functionally, CP affects a child's ability to perform age-appropriate activities such as standing, walking, and maintaining balance. Within spastic CP, balance impairments are highly prevalent due to deficits in postural control, sensory integration, and muscle coordination. Such impairments increase the risk of falls and restrict participation in daily activities. Therefore, balance is a critical outcome to assess, in addition to gross motor function and joint range of motion.(Araújo et al., 2020)

One of the most frequent musculoskeletal deformities in spastic CP is equines foot, commonly resulting from tightness or contracture of the gastrocnemius-soleus complex (Sarathy et al., 2019). This condition significantly affects gait and postural alignment. In more severe cases, surgical interventions like Achilles tendon lengthening are required to improve ankle dorsiflexion and facilitate better gait mechanics (Tateuchi, 2019). However, even after surgery, many children continue to face functional limitations due to persistent muscle tightness, fascia restrictions, and poor motor coordination. Surgical correction addresses structural deformity but often fails to resolve underlying neuromuscular dysfunction. Studies have shown that recurrence of equine deformity post-surgery is not uncommon, with rates reported up to 43% in some cohorts, particularly among those with severe preoperative contractures or younger age at surgery. Additionally, muscle-tendon lengthening procedures can lead to significant and prolonged muscle weakness, which may impede functional recovery and necessitate extended rehabilitation periods. These findings

underscore the importance of comprehensive postoperative rehabilitation strategies that address not only the structural corrections but also the persistent neuromuscular impairments to optimise functional outcomes.(Sala et al., 1997)

Post-surgical rehabilitation is crucial in enhancing outcomes, and physiotherapy plays a central role in this process. Conventional physiotherapy aims to improve muscle strength, range of motion, balance, and gait through stretching, strengthening, and task-specific training(Jain et al., 2023). Despite its importance, standard physiotherapy may not fully address deep soft tissue restrictions and altered fascial dynamics. In some cases, progress may plateau due to residual stiffness and abnormal tone, which can limit functional recovery.(Kilbride & McDonnell, 2000)

Myofascial Release (MFR) is a manual therapy technique designed to reduce fascial restrictions, improve tissue extensibility, and restore functional mobility. It involves gentle, sustained pressure into the fascial system to release adhesions and improve neuromuscular function (Ajimsha et al., 2015a). In recent years, growing evidence has supported its use in children with spastic CP. For example, studies have shown that MFR may help reduce spasticity, improve joint mobility, and enhance gross motor function when added to conventional physiotherapy (Chen et al., 2022). However, there remains a lack of focused research on the use of MFR in the postoperative context, especially following Achilles tendon lengthening procedures.

To date, to our knowledge no studies have specifically explored the effect of integrating MFR into rehabilitation programs for children with CP, after Achilles tendon surgery. Given the complexity of CP-related impairments and the potential of MFR to enhance tissue mobility and motor outcomes, this study aims to address gap in this area.

1.2 Problem Statement

Cerebral palsy (CP) is a prevalent neurological disorder in children, characterised by motor impairments, abnormal muscle tone, and movement dysfunction (Patel et al., 2020). Globally, CP affects approximately 2 to 2.5 per 1,000 live births, making it the most common motor disability in childhood (McIntyre et al., 2022). In certain areas within the Middle East and North Africa (MENA) region, such as Al-Quseir City in Egypt, the prevalence of cerebral palsy has been reported to reach 3.6 per 1,000 live births, potentially due to limited access to maternal and neonatal care (Shehata et al., 2014).

In Palestine, particularly in the Gaza Strip, the true prevalence is unclear due to the lack of national registries; however, regional clinical data and observations suggest a notably high rate, especially in areas affected by limited healthcare access, poverty, and repeated conflict-related trauma.

In cases of spastic CP, equinus deformity is common, resulting in altered gait patterns and reduced mobility (Horsch et al., 2021). Surgical options, such as Achilles tendon lengthening, aim to correct equinus and improve ambulation. However, many children continue to face limitations in range of motion, muscle stiffness, and balance even after surgery and physiotherapy, which hinders their ability to perform daily functional tasks (Horsch et al., 2021).

Children with CP face long-term functional limitations that severely impact their daily activities and overall well-being, including decreased muscle strength, joint contractures, poor postural control, and impaired motor coordination (Mutlu et al., 2017). They often struggle with walking, climbing stairs, maintaining balance, and engaging in play or recreational activities, leading to dependence on caregivers and assistive devices (Sutapa et al., 2021). These impairments also restrict participation in educational and social contexts, contributing to social isolation, reduced self-esteem, and a lower quality of life (Maciver et al., 2019). Additionally, chronic movement difficulties and fatigue may reduce physical activity and exacerbate secondary health complications (Mahindru et al., 2023).

Despite the importance of post-operative physiotherapy, current rehabilitation strategies for children with CP, following Achilles tendon lengthening are often limited to

conventional techniques such as stretching, strengthening, and balance training. However, few studies have investigated the integration of advanced manual therapy techniques, particularly Myofascial Release (MFR), into post-surgical rehabilitation (Page, 2012). Most research either focuses on pre-operative conditions or lacks specificity in addressing fascial restrictions and biomechanical deficits that persist after surgery.

This gap in the literature limits our understanding of how combining MFR with standard physiotherapy may affect gross motor function, balance and range of motion (ROM), in pediatric CP patients. Without evidence-based protocols incorporating MFR, clinicians may miss critical opportunities to optimize recovery and improve long-term outcomes. Thus, this study seeks to evaluate the effectiveness of adding MFR to conventional physiotherapy on functional outcomes in children with CP, following Achilles tendon surgery in the Gaza Strip — a setting with unique challenges and an urgent need for enhanced rehabilitation solutions.

1.4 Objectives of the Study

1.4.1 General Objective:

To evaluate the effectiveness of adding Myofascial Release (MFR) to conventional physiotherapy on functional outcomes and balance in children with cerebral palsy following Achilles tendon lengthening surgery in the Gaza Strip.

1.4.2 Specific Objectives:

1. To evaluate the effectiveness of conventional physiotherapy on functional outcomes in children with cerebral palsy following Achilles tendon lengthening surgery in the Gaza Strip.
2. To evaluate the effectiveness of conventional physiotherapy on balance in children with cerebral palsy following Achilles tendon lengthening surgery
3. To evaluate the effectiveness of adding Myofascial Release (MFR) to conventional physiotherapy on functional outcomes and balance in children with cerebral palsy following Achilles tendon lengthening surgery.

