1.5 Research questions

1. Does conventional physiotherapy alone improve gross motor function, balance, and ankle range of motion (ROM) in children with cerebral palsy following Achilles tendon lengthening surgery?
2. Does the addition of Myofascial Release (MFR) to conventional physiotherapy result in greater improvement in gross motor function compared to conventional physiotherapy alone?
3. Does the addition of Myofascial Release (MFR) to conventional physiotherapy result in greater improvement in balance compared to conventional physiotherapy alone?
4. Does the addition of Myofascial Release (MFR) to conventional physiotherapy result in greater improvement in ankle range of motion (ROM) compared to conventional physiotherapy alone?

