1.7 Operational Definition of Key Terms

Cerebral Palsy (CP):

A group of permanent disorders affecting the development of movement and posture, causing activity limitations, that are attributed to non-progressive disturbances occurring in the developing fetal or infant brain. While the injury itself is non-progressive, the resulting neuromuscular and musculoskeletal impairments, such as tone abnormalities,

joint contractures, and motor coordination deficits, may evolve over time. (Blair & Cans, 2025; Panda et al., 2024)

Spastic CP:

The most common type of cerebral palsy, characterized by increased muscle tone (hypertonia), stiffness, and restricted joint movement.(Novak et al., 2012)

Equine's Deformity:

A musculoskeletal condition commonly observed in children with spastic CP, involving excessive plantarflexion of the ankle, which impairs gait and balance.(İğrek et al., 2022)

Achilles Tendon Lengthening Surgery:

A surgical procedure performed to release or elongate the Achilles tendon to correct equinus deformity and improve ankle dorsiflexion.

Conventional Physiotherapy:

A structured rehabilitation program including stretching, strengthening, gait training, and balance exercises delivered by a licensed physiotherapist.

Myofascial Release (MFR):

A hands-on manual therapy technique aimed at relieving fascial restrictions to improve range of motion, reduce pain, and enhance movement efficiency.(Ajimsha et al., 2015b)

Chapter Two: Conceptual Framework and Literature Review

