2.1.2 Dependent Variables

Gross Motor Function

This refers to a child's ability to perform large muscle activities, such as sitting, standing, and walking. It will be measured using the Gross Motor Function Measure (GMFM), a validated scale for children with CP.

[figure not shown]
Range of Motion (ROM)

Specifically focused on ankle dorsiflexion and plantarflexion, ROM will be measured using a goniometer to assess joint mobility post-surgery and throughout rehabilitation. Improved ROM is essential for better gait and balance.

Balance:

The ability to maintain upright posture and stability during static and dynamic tasks. It will be measured using the Pediatric Balance Scale (PBS), a validated tool for young children with CP.

In this study, the independent variables—CPT and MFR—are expected to influence the dependent outcomes: gross motor function, balance, and ankle ROM. MFR is hypothesized to enhance the structural readiness of muscles and fascia, reducing tone and improving tissue mobility. This, in turn, may augment the efficacy of CPT by enabling more effective execution of strengthening, balance, and gait exercises. The synergistic combination is thus anticipated to yield greater improvements in functional outcomes compared to CPT alone.

Conceptual framework (Self developed)

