3.1 Study design

A single-blind randomized controlled trial (RCT) will be conducted to evaluate the effect of adding Myofascial Release (MFR) to conventional physiotherapy on functional outcomes in children with cerebral palsy after Achilles tendon surgery. Participants will be randomly assigned to either an intervention group (MFR + physiotherapy) or a control group (physiotherapy only). Assessments will be conducted at baseline and after 8 weeks of intervention.

Flow Diagram

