3.7.2 Intervention Group: Myofascial Release + Conventional Physiotherapy

Duration: 8 weeks

Frequency: 3 sessions per week

Session Duration: 60 minutes

Intervention Content:

The intervention will be conducted over a period of 8 weeks, with three sessions per week, totaling 24 sessions. Each session will last approximately 60 minutes, divided as follows:

45 minutes for Conventional Physiotherapy (CPT), described above

15 minutes for Myofascial Release (MFR)

Myofascial Release (MFR):

MFR will be administered by a physiotherapist using 4 selected techniques based on individual patient needs and tissue restrictions. Each MFR session will focus on releasing soft tissue restrictions in key muscle and fascial structures involved in gait and postural control in children with spastic cerebral palsy, particularly post Achilles tendon lengthening surgery.

The selected MFR techniques will be drawn from evidence-based protocols described in advanced myofascial release manuals and include:

1. Cross-Hand Release
2. Plantar Fascia Release
3. Gastrocnemius–Soleus Complex Release
4. Hamstring Fascial Lengthening

Each technique will be applied for 2–3 minutes, with gentle, sustained pressure held until tissue "melting" or release is palpated. Sessions will be performed in a calm, supportive environment, ensuring that the child is relaxed and comfortable throughout the treatment.

All sessions will be individualized based on functional level and tolerance, and monitored for consistency and safety.

Rationale: MFR may help release fascial restrictions, improve tissue mobility, reduce muscle tone, and promote better joint ROM and gross motor function—especially after surgical correction.

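### Specific objectives 1 and 2 ask for the effectiveness of conventional physiotherapy, but both arms receive it, so the trial cannot identify that effect

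*Combined protocol and SAP*

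**What the plan says.** Section 1.4.2 lists three specific objectives. The first is "To evaluate the effectiveness of conventional physiotherapy on functional outcomes in children with cerebral palsy following Achilles tendon lengthening surgery". The second is "To evaluate the effectiveness of conventional physiotherapy on balance in children with cerebral palsy following Achilles tendon lengthening surgery". The third concerns the addition of MFR to physiotherapy and uses the same term, effectiveness. Research question 1 in section 1.5 runs parallel to the first two: "Does conventional physiotherapy alone improve gross motor function, balance, and ankle range of motion (ROM". The conceptual framework in section 2.1.2 also treats physiotherapy as a causal factor: "the independent variables—CPT and MFR—are expected to influence the dependent outcomes: gross motor function, balance, and ankle ROM".

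Section 3.1 sets up two randomised arms, physiotherapy with MFR and physiotherapy alone, and states: "Assessments will be conducted at baseline and after 8 weeks of intervention". The control programme (section 3.7.1) is 45 minutes, three times a week, for 8 weeks. The MFR arm (section 3.7.2) has the same frequency and duration, with sessions made up of "45 minutes for Conventional Physiotherapy (CPT), described above" and 15 minutes of MFR.

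Section 3.11 plans two kinds of inferential test: pre/post comparisons within each group (paired t or Wilcoxon signed-rank) and comparisons of change between groups (independent t or Mann-Whitney). It does not link either kind to a particular objective.

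**The concern.** Effectiveness is a causal term. It asks what the children would have gained without the physiotherapy, and nobody in this trial goes without it. The between-group test serves objective 3 and research questions 2 to 4. That leaves the within-group test as the only planned analysis that could be directed at objectives 1 and 2.

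The within-group test is valid for the hypothesis that the mean change is zero, but it says nothing about the cause of a change. The children are 2 to 5 years old and within 3 months of tendon surgery (section 3.4), so change over 8 weeks from healing, development or familiarity with the assessments is plausible. The document does not treat the impairments as fixed: section 1.7 says that tone abnormalities, "joint contractures, and motor coordination deficits, may evolve over time". Nowhere does it label the within-group results as descriptive or mention the missing comparator.

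At stake is a report that credits physiotherapy with whatever significant improvement appears between the two visits. Nothing in the test output would warn the reader.

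**Working it through.** **Inputs from the document.** Two arms (3.1); 20 children per arm (3.5); the same scheduled physiotherapy in both arms, 24 × 45 min = 18 h (3.7.1, 3.7.2), with total session time of 24 × 60 min = 24 h in the MFR arm; two assessments (3.1, 3.6.2); significance level 0.05 (3.11).

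**Assumptions.** Two-sided testing (sidedness is not stated), no dropout, normally distributed changes. The document gives no figure for change without physiotherapy, so a range is used below. It also contains no calculation on this point to reproduce.

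**Step 1: what the design can estimate.** Let *r* be the mean 8-week change without physiotherapy, *c* the physiotherapy effect and *m* the added MFR effect.

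- Control arm: mean change = *r* + *c*
- MFR arm: mean change = *r* + *c* + *m*

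The coefficient rows for (*r*, *c*, *m*) are (1, 1, 0) and (1, 1, 1): rank 2 for three unknowns. Subtracting the first line from the second gives *m*, so the MFR effect is estimable. No combination of the two lines isolates *c*; only the sum *r* + *c* is available. This holds whatever the value of *r*.

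**Step 2: the threshold of the within-group test.** With n = 20 and 19 degrees of freedom, the critical t is 2.093. The smallest significant observed mean change is 2.093 / √20 = 0.468 SD of the change score, whatever produced it.

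**Step 3: how often the test is significant when *c* = 0.** The t statistic is noncentral with parameter *r* × √n, where *r* is in SDs of the change score. The Wilcoxon figures come from 10,000 simulated trials per value.

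| Assumed *r* | Paired t, n = 20 | Wilcoxon, n = 20 | Paired t, n = 40 |
|---|---|---|---|
| 0 | 5.0% | 5.2% | 5.0% |
| 0.2 | 13.6% | 12.7% | 23.5% |
| 0.3 | 24.7% | 24.1% | 45.7% |
| 0.5 | 56.5% | 53.2% | 86.9% |
| 0.8 | 92.4% | 90.9% | 99.9% |
| 1.0 | 98.9% | 98.4% | 100.0% |

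The rejection rate depends only on *r* + *c*. A physiotherapy effect of 0.5 SD with no background change would give the same 56.5% as a background gain of 0.5 SD with no physiotherapy effect. A larger sample does not help: it makes a significant result more likely without making it more attributable to physiotherapy.

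**The case against.** The strongest reply is that the trial is about MFR. The general objective, objective 3, research questions 2 to 4 and the between-group test all concern the add-on contrast, and the hypothesis in the conceptual framework is that the combination does better than physiotherapy alone. Objectives 1 and 2 are in effect one question split by outcome, and research question 1 could be read as asking only whether the control arm changes, which the paired test does answer. Section 3.11 draws no causal conclusion, so the harm arises only if the within-group result is used for these objectives. The percentages rest on assumed gains, and background change could also go the other way: section 1.1 mentions recurrence of equinus of up to 43% in some cohorts and prolonged weakness after lengthening.

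Much of this stands, and it limits the point. The main comparison is intact, the planned tests are not wrong in themselves, and the percentages are not an expected error rate. Background decline is possible too; it would hide a real physiotherapy effect, which is the same failure to identify *c* in the other direction. What the reply does not remove is the wording of objectives 1 and 2. They use the same causal term as objective 3, and the document offers no other analysis for them and no caution about interpretation.

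**Conclusion.** The concern holds. Two of the three specific objectives, and research question 1 if read causally, name an effect that this design cannot identify. That conclusion follows from the arms and the visit schedule alone and needs no assumed number.

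The consequence for error rates is illustrative. With no physiotherapy effect and assumed background gains of 0.2 to 1.0 SD of the change score, the control-arm paired t-test is significant in 14% to 99% of trials, against 5% when there is no background change. The problem is one of identification, not power. The general objective, objective 3 and research questions 2 to 4 are not affected by it. The mismatch should be corrected, but it does not undermine the trial's main comparison.

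**What to change.** - **Sections 1.4.2 and 1.5:** reword objectives 1 and 2 and research question 1 along the lines of: *to describe the 8-week change in [outcome] under conventional physiotherapy*.
- **Section 3.11:** add: *Within-group results (mean change with 95% CI for each arm) are descriptive and will not be interpreted as the effect of conventional physiotherapy. Conclusions on effectiveness rest only on the randomised between-group difference in change, reported with its 95% CI.*
- **Section 2.1:** for consistency, describe physiotherapy as the background treatment common to both arms and MFR as the factor under test. This edit is helpful but secondary, since that section sets no test.

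The cost is wording only: no extra children, visits, data or arm. The sponsor gives up an effectiveness claim for conventional physiotherapy that the design could not have supported.

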1.5 Research questions

1. Does conventional physiotherapy alone improve gross motor function, balance, and ankle range of motion (ROM) in children with cerebral palsy following Achilles tendon lengthening surgery?
2. Does the addition of Myofascial Release (MFR) to conventional physiotherapy result in greater improvement in gross motor function compared to conventional physiotherapy alone?
3. Does the addition of Myofascial Release (MFR) to conventional physiotherapy result in greater improvement in balance compared to conventional physiotherapy alone?
4. Does the addition of Myofascial Release (MFR) to conventional physiotherapy result in greater improvement in ankle range of motion (ROM) compared to conventional physiotherapy alone?

1.6 Context of the Study

Sociodemographic Context:

The Gaza Strip, a densely populated region with over 2.3 million inhabitants, faces numerous socioeconomic challenges due to prolonged political instability, blockade, and recurrent conflicts. More than 70% of the population are refugees, and a significant proportion lives below the poverty line. Children with disabilities, including those with CP, face multiple barriers in accessing education, healthcare, and social inclusion. Limited community awareness and stigmatization further contribute to their marginalization. The socioeconomic hardships often lead to reduced family resources, transportation difficulties, and limited parental engagement in rehabilitation services.

Palestinian Healthcare System:

The Palestinian healthcare system in Gaza is composed of three main providers: the Ministry of Health (MoH), the United Nations Relief and Works Agency for Palestine Refugees in the Near East (UNRWA), and non-governmental organizations (NGOs). While efforts are made to offer rehabilitation services for children with disabilities, the sector suffers from chronic underfunding, shortage of specialized staff, outdated equipment, and limited access to advanced physiotherapy modalities. The majority of rehabilitation services are provided by NGOs with external funding, and continuity of care is often interrupted by supply shortages or unstable security conditions. These challenges underscore the need for cost-effective, evidence-based interventions—such as combining Myofascial Release (MFR) with conventional physiotherapy—to optimize functional outcomes for children with CP post-surgery.

